2. STUDY OBJECTIVES

2.1 **Primary Objectives**

• To evaluate the safety and tolerability of SB-913.

2.2 Secondary Objectives

- To evaluate change from Baseline over time in the following assessments:
 - IDS activity in blood.
 - GAG testing in urine.
 - Frequency of ERT administration.
- AAV2/6 clearance.

2.3 Exploratory Objectives

- To evaluate change from Baseline over time in the following assessments:
 - o GAG levels in tissues (including blood, liver tissue, and cerebrospinal fluid [CSF]).
 - Gene modification at the albumin locus in the liver.
 - Imaging, functional, and neurocognitive testing related to MPS II.
 - Immune response to AAV 2/6, ZFNs and IDS.

From consenting subjects, residual samples may be used for future research objectives. Such future research objectives may include analysis of biomarkers of severity of disease, response to therapy (e.g. cytokines, soluble cell surface proteins, soluble receptors), and functional improvements (e.g., neurological function, musculoskeletal function), as well as determination of AAV virus inhibition, function, immunogenicity, or pharmacodynamics (e.g., antibodies, soluble receptors, AAV viral receptor inhibitors, cytokines, co-existing alternate serotype antibodies). For more details, refer to the Study Reference Manual.
3. STUDY DESIGN

3.1 Overview

This is a Phase 1/2, multicenter, open-label, single-dose, dose-ranging study with sequentially enrolled age cohorts: age ≥ 18 (adult cohorts 1 through 4), age 12-17 (pediatric cohorts 5 and 6), and age 5-11 (pediatric cohorts 7 and 8). Subjects who satisfy all inclusion/exclusion criteria are eligible to participate in this study.

3.2 Number of Subjects

Up to a total of 32 subjects will be enrolled in this study.

3.3 Dose

The doses of SB-913 selected for evaluation in this study are:

Cohort	ZFN 1 (SB-47171)	ZFN 2 (SB-47898)	hIDS Donor (SB-IDS)	Total rAAV
	(vg/kg)	(vg/kg)	(vg/kg)	(vg/kg)
1	5.00E+11	5.00E+11	4.00E+12	5.00E+12
2	1.00E+12	1.00E+12	8.00E+12	1.00E+13
3	5.00E+12	5.00E+12	4.00E+13	5.00E+13
4	1.20E+13	1.20E+13	9.60E+13	1.20E+14
5	5.00E+12	5.00E+12	4.00E+13	5.00E+13
6	TBD	TBD	TBD	TBD
7	TBD	TBD	TBD	TBD
8	TBD	TBD	TBD	TBD

3.4 Study Duration

The duration of study participation will be approximately 39 months for each subject (see Figure 9), divided into approximately 3 months for Screening followed by 36 months for treatment and study follow-up.

Figure 9. Schema of Study Visits.

Upon completion of the study, subjects will be asked to participate in a separate Long-term Follow-Up (LTFU) Study to monitor the long-term safety of SB-913. To alleviate study burden, study subjects may participate in the LTFU Study after at least 12 months of follow-up in this study. Study participants who wish to enroll in the LTFU Study with less than 12 months of follow-up in this primary study may be considered on a case-by-case basis at the judgement of the Principal Investigator and after consultation with the Sponsor.

3.5 Study Schedule

Subjects who satisfy all eligibility criteria will be enrolled into one of the following treatment cohorts:

Cohort #	Age Range (y)	Total Dose (vg/kg)	# Subjects
1	≥18	5.00E+12	2
2	≥18	1.00E+13	2
3	≥18	5.00E+13	2
4	≥18	1.20E+14	2
5	12-17	5.00E+13	2
6	12-17	TBD	2
7	5-11	TBD	2
8	5-11	TBD	2

Two subjects will be enrolled in each cohort, and will be dosed at least 4 weeks apart. SMC review occurs after at least 4 weeks of safety data is available from 2 subjects in each cohort.

The pediatric cohorts will be enrolled only after review of cumulative adult safety data by the SMC (see Section 12.3). The starting dose for pediatric cohorts 6 through 8 will be decided based on SMC review of study data, and must meet pre-defined safety criteria (see Pediatric Dosing).

Approximately 2 additional subjects may be added to any age cohort after SMC review of study data if safety criteria are met (see Safety Monitoring Committee), with up to a total of 32 subjects in the study.

TBD, to be determined based on SMC Review *will be enrolled if dose adjustment is indicated after SMC Review of study data

Figure 10. Schema of Cohort Enrollment.

Blue box = adult subjects age \geq 18 years; purple box = pediatric subjects age 12-17; green box = pediatric subjects age 5-11; orange box = SMC review; dashed orange line = SMC recommendation on pediatric dosing.

Subjects who received ERT prior to study enrollment will continue to receive ERT during the study and remain on their current schedule per standard of care unless they undergo ERT withdrawal (see Section 11.4). However, ERT will be omitted during the week of the SB-913 infusion to facilitate accurate baseline testing (e.g.; of GAG levels in urine, blood, and of IDS activity in blood) and to allow a week free of ERT after the SB-913 infusion.

To minimize the potential immune response to the AAV capsid protein, the engineered ZFNs, or the endogenous IDS, and to preserve hepatic function, prednisone or equivalent corticosteroid will be administered prophylactically starting 2 days prior to SB-913 infusion and will be tapered over a period of approximately 20 weeks (see Appendix 3).

The 3 components of SB-913 (ZFN1, ZFN2, and hIDS Donor) will each be added to 200 mL of diluent (refer to the Pharmacy Manual) and adjusted to 0.25% human serum albumin. Total infusion volumes will depend on a subject's cohort assignment and body weight (kg). IV infusions will be administered while the subject is in the hospital or acute care facility (refer to the Pharmacy Manual).

The subject will remain in the hospital or acute care facility for at least 24 hours after completion of SB-913 infusion for observation, and will be discharged when all AEs and vital signs (temperature, heart rate, respiratory rate, and blood pressure) are stable.

After being discharged from the hospital or acute care facility, study visits are scheduled on Day 7; Weeks 2, 4, 6, 8, 12, 16, 20, 24, 28, 32, 36, 40, 44, 48, and 52; and Months 15, 18, 21, 24, 27, 30, 33, and 36 (see Section 6 and Appendix 1).

Liver function tests (aspartate aminotransferase [AST], alanine aminotransferase [ALT], total and direct bilirubin, alkaline phosphatase, LDH, albumin, and total protein levels) will be conducted for evaluation of AAV mediated immunogenicity twice a week during the first 20 weeks after SB-913 infusion and may be conducted at home if the subject is remote. Blood samples for liver function tests will be drawn 2-4 days apart when possible, except for the first week when they will be drawn on the Day 1 and Day 7 visits. Liver function tests will subsequently be conducted at all study visits.

Previous studies with IV AAV8 FIX gene therapy have shown that liver transaminitis due to AAV immunogenicity occurs between 2 and 9 weeks after infusion and resulted in loss of FIX expression, and that rapid institution of prednisone can control this immunogenicity. If in spite of pretreatment with prednisone or equivalent corticosteroid in this study there is evidence of transaminitis, the dose of prednisone or equivalent corticosteroid will be increased on a case-by-case basis, and liver function will be assessed twice a week until normalization of liver enzymes, and then per protocol thereafter.

4. SUBJECT SELECTION

4.1 Inclusion Criteria

Subjects must meet all of the following criteria to be included in the study:

- 1. Signed informed consent.
- 2. \geq 5 years of age:
 - a) Adult cohorts 1 through $4: \ge 18$ years of age;
 - b) Pediatric cohorts 5 and 6: 12 to 17 years of age; and
 - c) Pediatric cohorts 7 and 8: 5 to 11 years of age.
- 3. Clinical diagnosis of MPS II (based on evidence of hepatosplenomegaly, dysostosis multiplex by X-ray, valvular heart disease, or obstructive airway disease); IDS deficiency confirmed by gene sequencing.
- 4. Sexually mature subjects must agree to use a barrier contraceptive method for prevention of AAV transfer as follows: for female subjects this means that the subjects' partners must use a condom from dosing with SB-913 until at least 3 consecutive plasma samples after administration of SB-913 are negative for AAV2/6; for male subjects this means that the subjects must use a condom and must refrain from sperm donation from the time of SB-913 administration until at least 3 consecutive semen samples after administration of SB-913 are negative for AAV2/6. Additionally, female subjects of child-bearing potential must consent to use a highly effective method of contraception.
- 5. Magnetic resonance imaging (MRI) negative for liver mass as read by a radiologist.

4.2 Exclusion Criteria

Subjects who meet any of the following criteria will be excluded from participating in the study:

- 1. Known to be unresponsive to ERT.
- 2. Neutralizing antibodies in serum (immune response) to AAV2/6.
- 3. Serious intercurrent illness or clinically significant organic disease (unless secondary to MPS II) such as cardiovascular, hepatic, pulmonary, neurologic, or renal disease.
- 4. Receiving antiviral therapy for hepatitis B or C, or with active hepatitis B (HBV DNA positive or HBV surface antigen positive) or hepatitis C (HCV RNA viral load) or human immunodeficiency virus (HIV)-1/2 (HIV RNA viral load or HIV antibody positive); to be considered negative for hepatitis C after treatment of an active HCV infection, viral assays in 2 samples collected at least 6 months apart must be negative.
- 5. Lack of tolerance to idursulfase treatment with significant infusion-associated reactions (IARs) or occurrence of anaphylaxis.
- 6. Polymorphisms in the ZFN-targeted region of the albumin locus.
- 7. Liver fibrosis score of 3 or 4 on a 0 to 4 point scale (Desmet et al. 1994) if subject has had a liver biopsy within 2 years of Screening.
- 8. Markers of hepatic dysfunction as evidenced by one or more of the following:
 - a) Platelet count $<100,000/\mu$ L

- b) Albumin $\leq 3.2 \text{ g/dL}$
- c) Total bilirubin >1.5 x upper limit of normal (ULN) and direct bilirubin ≥0.5 mg/dL
- d) Alkaline phosphatase >2.0 x ULN
- e) ALT or AST > 2.0 x ULN
- 9. Creatinine $\geq 1.5 \text{ mg/dL}$.
- 10. Weight < 20 kg at Screening visit.
- 11. Pregnant or breastfeeding female.
- 12. Contraindication to the use of corticosteroids.
- 13. Current treatment with systemic (IV or oral) immunomodulatory agent or steroid use (topical treatment allowed, e.g., for asthma or eczema).
- 14. History of active malignancy in past 5 years (non-melanoma skin cancer or cervical cancer *in situ* permitted).
- 15. Participation in prior investigational drug or medical device study within the previous 3 months.
- 16. Prior treatment with a gene therapy product.
- 17. History of alcohol or substance abuse that in the opinion of the Principal Investigator may interfere with study compliance.
- 18. History of therapeutic non-adherence.
- 19. Elevated or abnormal circulating α -fetoprotein (AFP).
- 20. Any other reason that, in the opinion of the Principal Investigator or Medical Monitor, would render the subject unsuitable for participation in the study.

5. INFORMED CONSENT

Informed consent must be obtained from the subject as institutional policy allows before any study-related screening activity is undertaken that is not part of routine care. Informed consent may be obtained separately for Screening blood tests only (to determine eligibility based on neutralizing antibodies to AAV 2/6 and single-nucleotide polymorphism [SNP] analysis) prior to obtaining full study Informed Consent, if allowed by the local institutional review board (IRB) or institutional ethics committee (IEC) or equivalent. The subject's legally authorized representative may also provide informed consent for subject participation if allowed by the local IRB/IEC or equivalent. The Principal Investigator or designated personnel will explain to each subject or the subject's legally authorized representative the nature of the study, its purpose, the procedures, the expected duration, alternative therapies available, and the benefits and risks of participation. The subject or the subject's legally authorized representative will receive an information and consent document, with the opportunity to ask questions, and will be informed that participation is voluntary, and that the subject can withdraw from the study at any time without any impact upon the subject's future clinical care. The subject or the subject's legally authorized representative will receive a copy of the signed and dated written informed consent form and any other written information required for the study. Each subject will be re-consented at the time of any informed consent amendment, as applicable, and will be provided a copy of the signed and dated revised consent form.

6. STUDY METHODOLOGY

Prior to initiation of this study, the study site shall be approved by the IRB/IEC or equivalent. Subjects must be willing to participate in all study procedures related to this protocol. The following sections describe all study procedures. Additional detailed instructions will be provided in the Study Reference Manual, Laboratory Manual, and Pharmacy Manual. A table of all study procedures is presented in the Schedule of Events (see Appendix 1).

6.1 Screening

The objective of the Screening visits is to identify subjects who meet the stated inclusion and exclusion criteria and who are willing and able to participate in the study.

Screening may take up to approximately 3 months and may be performed across several visits.

- Obtain a signed and dated subject informed consent form and authorization document to use and disclose medical information prior to performing any study-specific procedures.
- Obtain a complete medical history.
- Review and record concomitant medications.
- Review the inclusion and exclusion criteria.
- Assign a subject number.
- Collect demographic information.
- Physical examination.
- Vital signs.
- Assessment of AEs.
- ERT administration log.
- 12-lead electrocardiogram (ECG).
- Echocardiogram (ECHO).
- Chest x-ray.
- Pregnancy test (for females of childbearing potential only).
- Clinical laboratory tests.
- Liver panel.
- MPS II gene sequencing.
- SNP analysis.
- Viral load.
- Neutralizing antibodies to AAV2/6.

- GAG testing in urine (collect samples on 3 separate days, each collection occurring at least 7 days after the previous, and all collections occurring at least 7 days after ERT administration [+/-1 day] but prior to the next ERT infusion).
- IDS / GAG testing in blood (collect 7 days after ERT administration [+/-1 day]).
- Circulating AFP level.
- Pulmonary function tests (PFTs).
- VABS-II (Vineland Adaptive Behavior Scales) test.
- Neurocognitive abilities assessment.
- MRI of liver.

Subjects may be re-screened in the judgement of the Principal Investigator and after consultation with Sangamo. For subjects who are re-screening for participation in the study, the following assessments performed in the previous 6 months may be used for evaluation of inclusion/exclusion criteria at the judgement of the Principal Investigator:

- ECHO.
- Chest X-Ray.
- PFTs.
- MRI of liver and/or brain and cervical spine.

Further, genetic marker analysis including SNP analysis and MPS II sequencing will not be repeated as results of these assessments do not change over time.

6.2 Subject Enrollment

Before a subject is assigned to a dose cohort, the study site personnel must verify that the subject fulfills all eligibility criteria.

The pediatric cohorts will be enrolled only after review of cumulative adult safety data by an independent, external SMC.

6.3 Baseline

Baseline assessments will be performed within 21 days prior to SB-913 infusion.

In subjects receiving ERT, ERT shall be withheld during the week of the administration of SB-913 to enable accurate baseline testing.

- Review and record concomitant medications.
- Physical examination.
- Vital signs.
- Assessment of AEs.
- ERT administration log.
- Joint range of motion (JROM).

- Neurologic cranial nerve exam and muscle strength testing of the upper extremities.
- 12-lead ECG.
- Pregnancy test (for females of childbearing potential only).
- Clinical laboratory tests.
- Liver panel.
- GAG testing in urine.
- IDS / GAG testing in blood.
- Vector genome PCR in plasma, saliva, urine, stool, and semen (males only).
- PFTs.
- 6-minute walk test (6MWT).
- Neurocognitive abilities tests by WASI-II (Wechsler Abbreviated Scale of Intelligence), WPPSI-IV (Wechsler Preschool and Primary Scale of Intelligence), or BSID-III (Bayley Scales of Infant Development), and by VABS-II.
- MRI of brain and cervical spine.
- Adrenocorticotropic hormone (ACTH) stimulation (cosyntropin) test (prior to prednisone or equivalent corticosteroid).
- Liver biopsy.
- Lumbar puncture.
- Immunogenicity assays.
- Prednisone or equivalent corticosteroid administration (starting 2 days before SB-913 infusion).

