8.1.3 Carcinogenicity

There is a risk that people who receive gene transfer may develop tumors derived from their genetically modified cells. This risk has been seen with viral gene transfer vectors that integrate randomly into the cellular DNA where they may affect genes controlling cell proliferation. The rAAV2/6 vector donor will integrate specifically in the albumin ZFN DSB site. In toxicity studies, no tumors were identified. For evaluation of liver carcinogenicity the current study adopts the hepato-cellular carcinoma (HCC) screening recommendation for high risk subjects (e.g., chronic hepatitis C or B), which includes monitoring AFP and liver MRI. Liver biopsy will be performed if there is an abnormal AFP and a >2 cm mass in the liver (El-Serag & Davila 2011).

8.2 **Prednisone (or Equivalent Corticosteroid)**

Prednisone is a glucocorticoid. Glucocorticoids are adrenocortical steroids, both naturally occurring and synthetic, which are readily absorbed from the gastrointestinal tract.

The following adverse reactions have been associated with the use of glucocorticoids:

- Thinning of bones (osteoporosis), which may lead to fractures or compressions, especially true of vertebral bodies (backbone).
- Loss of blood supply to bones (aseptic necrosis), which may cause severe bone pain, fractures (especially of the hip and shoulder), and which may require surgical correction.
- High blood pressure (hypertension).
- Increased pressure in the eye (glaucoma).
- Permanent clouding of vision in one or both eyes (cataracts).
- Weight gain with increased appetite and fluid retention.

- Facial fullness.
- Increase in body hair and acne, and tendency to easy bruising and thinning of the skin.
- Increased risk of infections while on high dose continuous steroid therapy.
- Interference with growth.
- Muscle cramps and joint pain.
- Changes in the menstrual cycle.
- Elevations in blood sugar (diabetes).
- Suppression of adrenal glands' ability to make necessary cortisone at times of stress (adrenal insufficiency).
- Irritation of stomach and esophagus with possible ulcer type symptoms and, rarely, bleeding.
- Emotional disturbances.

Dietary guidelines will be provided to subjects while on prednisone or equivalent corticosteroid to help alleviate some of the side effects including blood sugar elevation, associated with the use of glucocorticoids (refer to the Study Reference Manual).

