10.3 Recording of an Adverse Event

The Principal Investigator is responsible for evaluating all AEs, obtaining supporting documents, and determining that documentation of the event is adequate. He/she is responsible for determining the severity of the AE and its relationship to the investigational drug. The Principal Investigator may delegate these duties to sub-investigators but must assure that these sub-investigators are qualified to perform these duties under the supervision of the Principal Investigator.

All AEs will be recorded in the subject's CRF. The detailed description of the event will include appropriately graded severity of the AE and its relationship to the investigational product. Severity will be categorized by toxicity grade according to the Common Terminology Criteria for Adverse Events (CTCAE) Version 4.03.

AEs not listed in the Common Terminology Criteria for Adverse Events version 4.03 will be evaluated by using the following criteria:

- Grade 1, Mild: Symptoms cause no or minimal interference with usual social and functional activities.
- Grade 2, Moderate: Symptoms cause greater than minimal interference with usual social and functional activities.
- Grade 3, Severe: Symptoms cause inability to perform usual social and functional activities.
- Grade 4, Potentially Life-threatening: Symptoms cause inability to perform basic self-care functions OR medical or operative intervention indicated to prevent permanent impairment, persistent disability, or death.
- Grade 5: Outcome of AE is death.

The relationship of the AE to the investigational drug will be determined by the Principal Investigator. Any AE that does not meet the definition of a suspected AR will be categorized as Not Related.

Any Grade 3 and 4 clinical laboratory results that represents an increase in severity from Baseline will be reported as an AE if it is not associated with a diagnosis already reported on the CRF. A Grade 1 or 2 clinical laboratory abnormality should be reported as an AE only if it is considered clinically significant by the Principal Investigator.

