#### 4.3 Assessment Windows

For the purpose of listing and summarizing data, the time-in-study for each subject observation will be defined using study days, weeks and months. Such days will be measured relative to Day 0, the day on which SB-913 is infused. Because protocol-specified visits (e.g., Week 16) will not necessarily occur on the same study day for all subjects, study visits will be defined through the use of windows. Study visits will have windows as per the following schema:

Data will be summarized based on the CRF (Study Visit) in which it was collected.

Baseline will be defined as the last pretreatment value during the screening period except for the GAG/IDS values. For the GAG/IDS test, baseline will be calculated using the mean of all prior dosing values. If more than one assessment exists within a single visit window, the value closest to the protocol study visit will be used for summary and analysis purposes. Data from all assessments will be listed.

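### Baseline laboratory tests and vital signs may be taken after prednisone has started, and SAP 4.3 would then prefer that value to a steroid-free Screening value

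*Protocol*

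**What the plan says.** Protocol 6.3 states that "Baseline assessments will be performed within 21 days prior to SB-913 infusion". The same list of Baseline procedures includes "Prednisone or equivalent corticosteroid administration (starting 2 days before SB-913 infusion". One item in the list is placed before the steroid: "Adrenocorticotropic hormone (ACTH) stimulation (cosyntropin) test (prior to prednisone or equivalent corticosteroid". Appendix 1 repeats that condition for the ACTH test and sets none for clinical laboratory tests, liver panel or vital signs.

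Protocol Appendix 3 plans, from Day -2, 60 mg/day in the 55 kg and higher rows, 50 down to 30 mg/day in the 50 to 30 kg rows, and 1 mg/kg below 30 kg. The dose falls from Week 2 and stops at Week 20.

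SAP 4.3 says: "Baseline will be defined as the last pretreatment value during the screening period except for the GAG/IDS values". For GAG and IDS, "baseline will be calculated using the mean of all prior dosing values". SAP 7.3 presents laboratory data as change from baseline and in shift tables. SAP 7.4 presents vital signs as change from baseline. Protocol 8.2 lists high blood pressure and "Elevations in blood sugar (diabetes" among the reactions to glucocorticoids.

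**The concern.** Current systemic steroid use is an exclusion (Protocol 4.2, criterion 13), so Screening values should be free of steroid effect. A Baseline-visit value on Day -2 or Day -1 need not be. Where a subject has both, the SAP rule picks the later one.

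Glucose or blood pressure already raised by prednisone would then be the reference for the whole study. Rises in the steroid weeks would look smaller than they were, and a return to the usual level after the taper would look like a fall. In a laboratory shift table, glucose that was normal at Screening and high on Day -1 would show no shift if it stayed high, and an improvement if it returned to normal. Because visit timing can differ between subjects, a two-subject cohort could combine one on-steroid and one off-steroid baseline. A difference between dose cohorts could then reflect scheduling.

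**Working it through.** **1. Does the Baseline visit fall inside the SAP's screening period?** Protocol 3.4 divides participation into "approximately 3 months for Screening followed by 36 months for treatment and study follow-up", which leaves no separate interval for Baseline. SAP 5.4 lists the 6-minute walk as a baseline characteristic, yet Appendix 1 schedules that test at Baseline and not at Screening. The Baseline visit must therefore count. The SAP does not define pretreatment. Since SAP 4.4 counts study days from the first study drug administration, the natural reading is before SB-913, not before prednisone.

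**2. Exposed days.** Day -21 to Day -1 is 21 days. Prednisone is given on Day -2 and Day -1, so 2/21 = 9.5% of the window is exposed. Laboratory tests are not scheduled on Day 0 (Protocol 6.4, Appendix 1).

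**3. Chance that a cohort of two is affected.** The documents do not give the actual timing of Baseline visits, so the probability p that a subject's baseline is on prednisone is assumed. At least one of two affected: 1 - (1 - p)². Exactly one affected: 2p(1 - p).

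| Assumed p | At least one of two | Exactly one of two |
|---|---|---|
| 2/21 = 0.095 (even over the window) | 18% | 17% |
| 2/7 = 0.286 (even over the last 7 days) | 49% | 41% |
| 0.5 | 75% | 50% |

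Protocol 6.3 withholds ERT in the infusion week for the sake of baseline testing. Late visits are therefore plausible, but the text does not establish them.

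**4. Size and direction.** Let D be the amount by which prednisone has raised a value at baseline. Change from an on-prednisone baseline = change from an off-prednisone baseline - D, at every visit. To show the pattern, assume that the effect is proportional to dose and that SB-913 has none. For a subject of 55 kg or more on the planned taper, the off-prednisone change is (dose/60) × D:

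| Planned dose | Off-prednisone baseline | On-prednisone baseline | Mean, one of each |
|---|---|---|---|
| 60 mg (Day 1) | +1.00D | 0 | +0.50D |
| 30 mg (Week 2) | +0.50D | -0.50D | 0 |
| 15 mg (Weeks 3-16) | +0.25D | -0.75D | -0.25D |
| Stopped (Week 20 on) | 0 | -1.00D | -0.50D |

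With one of two subjects affected, the cohort mean is D/2 too low throughout. The documents give no value for D. If D for glucose were 20, 40 or 60 mg/dL (assumed), the error in the mean would be 10, 20 or 30 mg/dL.

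**5. How many later visits share the baseline dose?** SAP 7.3 schedules 19 chemistry time points after infusion, early termination aside: Day 1, ten weekly visits (Weeks 2, 4, 6, 8, 12, 16, 20, 24, 36, 48) and eight monthly visits (Months 15 to 36). On the planned taper, 1 (Day 1) is at the baseline dose, 6 (Weeks 2 to 16) are at reduced doses and 12 (Week 20 onward) are at or after the stop: 1 + 6 + 12 = 19.

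Separately, the first dose column ends at Day 0 in Protocol Appendix 3 and at Day 1 in SAP Appendix C. The two should be reconciled, but nothing above depends on it.

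**The case against.** The exposure is small. Only two window days are affected, and the manuals to which the protocol defers may already fix the timing of draws. Protocol 8.2 gives no onset time, so it does not show that glucose or blood pressure moves within 48 hours. Clean Screening values exist, all assessments are listed, actual values are summarised at each visit and prednisone is recorded. With two subjects per cohort and no hypotheses, a careful reader could spot a shifted baseline. A pre-steroid baseline also has a price: changes in the steroid weeks then combine SB-913 with prednisone.

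Most of this stands and limits the point to a minor one. The trade-off argument does not rescue the current rule. An on-steroid baseline isolates SB-913 only while the dose is unchanged, which for chemistry is one time point of 19. The current wording also does not choose an on-steroid baseline; it leaves the choice to scheduling.

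Four stronger readings are tempting and are not supported:

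- **Every blood pressure baseline is on prednisone, because vital signs are taken before infusion on Day 0.** SAP 4.3 confines baseline to the screening period and summarises by visit form, SAP 4.4 treats the dosing day as on or after dosing, and SAP 7.4 lists Day 0 apart from Baseline. Day 0 is probably not baseline, although the SAP never says so.
- **The primary endpoint is distorted.** Protocol 10.3 says "Any Grade 3 and 4 clinical laboratory results that represents an increase in severity from Baseline will be reported as an AE" (unless already covered by a reported diagnosis). A new Grade 3 result is an increase over any Baseline of Grade 0 to 2, so masking needs a Baseline already at Grade 3 or above. Nothing in the documents suggests that two days of prednisone would do that.
- **Blood counts are affected.** Protocol 8.2 lists no such effect.
- **The GAG and IDS endpoints are affected.** They are excepted from the last-value rule, and no steroid effect on them is described.

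**Conclusion.** The gap is real and minor. The protocol permits Baseline laboratory tests and vital signs on prednisone, and the SAP rule would select those values over earlier steroid-free ones. For glucose and blood pressure this could bias the change-from-baseline tables, and for glucose the shift tables as well, with an error of -D in each affected subject at every later visit. It rests on three conditions: a Baseline visit on Day -2 or Day -1, a steroid effect already present by then, and pretreatment meaning before SB-913. The first is a matter of scheduling that the documents leave open, and the size of the second is unknown. Adverse event reporting is unlikely to be affected.

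**What to change.** In SAP 4.3:

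- Define baseline for clinical laboratory tests (including the liver panel) and vital signs as the last value before the first corticosteroid dose. Start dates are on the concomitant medications page (Protocol 7.2), so the rule also works for subjects already dosed.
- State that Day 0 pre-infusion vital signs are a separate time point and not baseline.
- Flag any subject whose only Baseline-visit value was taken on corticosteroid.

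For subjects not yet dosed, extend the ordering that Protocol 6.3 and Appendix 1 already apply to the ACTH test to Baseline clinical laboratory tests, liver panel and vital signs. The liver panel is included because Appendix 1 lets it share the clinical laboratory sample, not because a steroid effect on it is documented.

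Cost: wording in two documents and no added tests. The usable window shrinks from 21 to about 19 days (21 - 2). Changes in the steroid weeks will reflect SB-913 plus the mandatory prednisone, which the tables should say. For a flagged subject the baseline falls back to an older Screening value, since Appendix 1 allows Screening up to 3 months before Baseline.
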